## 7 STATISTICAL METHODS

### 7.1 General Principles

The statistical package SAS® will be used to produce all summary tables, figures, and listings.

In general, categorical data will be presented using counts and percentages, whilst continuous variables will be presented using the number of patients, mean, standard deviation, median, minimum, and maximum. Denominators for calculation of percentages will be taken as the number of non-missing responses in the specified analysis population and treatment group unless otherwise stated, and percentages will be rounded to one decimal. Minima and maxima will usually be reported to the same level of accuracy as the raw data; means, medians and standard deviations will be presented to one further decimal place; standard errors (if presented) will be presented to 2 decimal places more than the raw data.

REP0112

Statistical Analysis Plan

All data recorded in the CRF will be listed.

Unless otherwise specified, the significance level used for statistical testing will be 5% and two-sided tests will be used.

## 7.2 Missing Data

All reasonable efforts will be made to reduce the rate of missing data, since any method used for imputation for missing observations would be based on untestable assumptions that likely would be invalid.

Patients will be informed that they have the right at any time to withdraw from further participation in the study (*withdrawal of consent*), without prejudice to their medical care, and without being obliged to state their reasons. However, the term *withdrawal of consent* should be used only when the patient no longer wishes to participate in the trial and no longer authorizes the investigators to make efforts to continue to obtain his/her outcome data. Ideally, if patients withdraw their consent, it should be done in writing.

During the consent process, patients will be also educated about the scientific relevance of their continued participation as well as the deleterious effect that missing data will have on trial integrity.

It is important to distinguish reasons for stopping randomized treatment (i.e., for non-adherence), from reasons to stop follow-up (i.e., for non-retention). While there are many appropriate reasons to discontinue randomized treatment, the only reasons to discontinue follow-up would be death or withdrawal of consent. Patients who have discontinued the study treatment but have not withdrawn consent should be followed to ensure that primary and secondary outcome measures are assessed.

Investigators will be trained about the importance of patient retention and full data capture. Also, all reasonable attempts should be made by the investigators to emphasize continued patient's participation for the full duration of the trial. If a patient fails to return to the center for a scheduled visit, all reasonable attempts should be made to contact the patient. To minimize missing data, if a patient cannot refer to the site for a planned follow-up visit, the investigator will try to obtain any relevant information from the patients, including documents/lab results available from local medical care.

Handling of missing data will be addressed for each summarization and analysis of data, as applicable, in sections of this SAP which describe summarization and analysis of data.

Appropriate descriptive statistics will be produced to quantify the amount of missing data to allow comparison between the treatment groups.

## 7.3 Methods for Multiplicity Correction in Analyses

If the primary analysis of the primary endpoint leads to rejection of the null hypothesis, the null hypotheses for the following secondary endpoints will be tested in a conditional sequential manner. The sequence in which these secondary endpoints will be tested is as follows:

1. AUC for serum C-peptide level during the first 4 hours of a MMTT, normalized by the number of IEQ/kg, at Day 365 ± 14 days after IAT.
2. Average daily insulin requirement at Day 365 ± 14 days after IAT.
3. Time course of C-peptide derived from the MMTT at Day 365 ± 14 days after IAT.
4. β-cell function as assessed by β-score at Day 365 ± 14 days after IAT.
5. The proportion of patients with HbA1c ≤ 6.5% at Day 365 ± 14 days after IAT.

REP0112

Statistical Analysis Plan

6. Cumulative number of severe hypoglycemic events from Day 75 ± 14 days to Day 365 ± 14 days after IAT.
7. The proportion of patients with HbA1c ≤ 6.5% at Day 365 ± 14 days after IAT **AND** free of severe hypoglycemic events from Day 75 ± 14 days to Day 365 ± 14 days after IAT, inclusive.

A null hypothesis will be rejected if and only if the primary analysis of that endpoint and all primary analyses of preceding primary and secondary endpoints result in a rejection of the respective null hypotheses. This procedure protects the family-wise false positive error rate at the overall one-sided 0.025 level.

#### **7.4 Disposition, Baseline Data, Concomitant Medications, Drug Exposure**

Summaries of disposition, baseline data, concomitant medications, and drug exposure will be produced using the screened, randomized, ITT, PP, and safety populations as noted in the following sections and will be presented by treatment group and overall.

##### **7.4.1 Patient Disposition**

The number of patients screened in total will be presented. The number of patients randomized and number and percentage of randomized patients who did not receive IAT, who were treated, who were included and treated/included and not treated/excluded from the safety population (with reason for exclusion [not randomized] presented as a percentage of patients screened in total only), who were included/excluded from the ITT population (with reason for exclusion), who were included/excluded from the PP population (with reason for exclusion), who completed the study, and who withdrew early from the study (with primary reason for early withdrawal) will be presented by treatment group and in total. The number and percentage of randomized patients who were included in the safety population will be summarized by treatment as received, or by treatment as randomized for those not treated. Fisher's exact test will be used to compare between treatment groups the proportion of randomized patients who did not receive IAT.

Screening data recorded for patients who do not proceed to transplant with study drug administration will be listed separately.

Patient disposition at each site will be presented by treatment group and in total, with the exception of there being no comparison between treatment groups of the proportion of randomized patients who did not receive IAT.

##### **7.4.2 Protocol Deviations**

Protocol deviations which exclude patients from the PP population (see Section 6 for definition) will be summarized by treatment group and in total. The number and percentage of ITT patients with at least one protocol deviation and with each type of protocol deviation (by classification and sub-classification) will be presented.

The summarization of protocol deviations will also be presented by site.

##### **7.4.3 Demographic data**

Demographic data will be presented for the ITT, PP, and safety populations. Summary statistics for age in years, height in centimeters, and weight in kilograms at screening, and gender, race, and ethnic origin will be presented by treatment group and in total.

##### **7.4.4 Specific Clinical History**

Specific clinical history data will be presented for the safety population. The number and percentage of safety patients with each type of pancreatectomy (total, completion), with each reason for pancreatectomy (chronic pancreatitis, recurrent acute pancreatitis), and with each

REP0112

Statistical Analysis Plan

primary etiology of disease (hereditary or genetic disease, alcohol, sphincter of odi dysfunction, pancreas divisum, idiopathic or unknown, other) will be presented by treatment group and in total.

The number and percentage of patients who had a completion pancreatectomy who had previous IAT and who had each type of prior partial resection (whipple (head) resection, distal pancreatectomy) will be presented by treatment group and in total.

The summarization of specific clinical history will also be presented by site.

Other non-chronic pancreatitis etiology (which are reasons for exclusion from the study) will be presented in a data listing.

#### 7.4.5 Significant Medical History

Significant medical history will be summarized for the safety population.

The number and percentage of patients reporting any significant medical history and any significant medical history which is ongoing at screening will be presented by treatment group and in total. In addition, the number and percentage of patients reporting an item of significant medical history (any and ongoing at screening) within each of the following 15 body systems will also be presented by treatment group and in total: general appearance; head, ears, eyes, nose and throat; cardiovascular; pulmonary; gastrointestinal; liver; renal; genitourinary; endocrine; immune/allergy; psychiatric; central nervous system; dermatologic; musculoskeletal; and other.

#### 7.4.6 Concomitant Medications

Concomitant medications will be summarized for the safety population.

Concomitant medications will be those medications taken at or after the time of the start of investigational product. Medications will be coded to standardized therapeutic classes and preferred terms using the WHO Drug Dictionary version as specified in the Data Management Plan associated with this protocol.

The number and percentage of patients using at least one concomitant medication and using at least one concomitant medication within each therapeutic class and preferred term will be presented by treatment group and in total.

#### 7.4.7 Investigational Product Exposure

Investigational product exposure will be summarized for the safety population.

The number and percentage of patients who did not receive investigational product (in total only), received continuous investigational product infusion, who completed investigational product infusion (7 days), and who prematurely and permanently discontinued investigational product (and by reason for premature and permanent discontinuation of investigational product) will be summarized by treatment group and in total.

Duration of investigational product infusion in hours, average rate of investigational product infusion in mL/hour, amount of investigational product infused in mL and in mg, and percentage of intended dose administered will be summarized descriptively by treatment group and in total.

- Duration of investigational product infusion in hours will be computed as the last infusion end date/time minus the first infusion start date/time plus 1 second and minus the total interruption time in hours, divided by 3,600 seconds per hour.
- Average rate of investigational product infusion to be summarized for a patient will be computed as the average of the infusion rates for all infusion bags which were started for the patient.
- Amount of investigational product infused in mL will be estimated for a given patient for each infusion bag as infusion rate in mL/hour multiplied by duration of investigational product infusion per bag (according to definition of investigational

REP0112

Statistical Analysis Plan

product infusion in hours but on a per bag basis), and will be estimated in total as the sum over all infusion bags of the amount of investigational product infused.

- Amount of investigational product infused in mg will be estimated for a given patient for each infusion bag or over all infusion bags as the amount of investigational product infused in mL multiplied by 11.00 mg/mL (per Section 6.1.4 of the study protocol).
- Percentage of intended dose administered will be computed as duration of investigational product infusion in hours divided by 168 hours, multiplied by 100, which is derived as follows.

Actual dose administered will be equal to:

$$(2.772 \text{ mg/kg}) \times (\text{body weight in kg}) \times (\text{duration of infusion in hours})$$

Intended dose will be equal to:

$$(2.772 \text{ mg/kg}) \times (\text{body weight in kg}) \times (168 \text{ hours})$$

The percentage of intended dose administered will be computed as:

$$(\text{actual dose administered}) / (\text{intended dose}) \times 100\%$$

$$= (\text{duration of infusion in hours}) / (168 \text{ hours}) \times 100\%$$

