### **Investigational Product**

The investigational drug will be reparixin or matching placebo. Reparixin will be administered as a continuous i.v. infusion into a (high flow) central vein at a dose of 2.772 mg/kg body weight/hour for 7 days (168hrs), starting approximately 12hrs (6-18 hrs) before pancreatic islet infusion. Placebo (0.9% w/v sodium chloride solution) will be infused at matching volume/rate.

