## 6. INVESTIGATIONAL PRODUCT

The Investigational Product will be either reparixin [R(-)-4-Isobutyl-alpha-methylphenylacetyl-methanesulfonamide] or matched placebo.

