## 6.2. DOSE, ROUTE AND SCHEDULE OF INVESTIGATIONAL PRODUCT ADMINISTRATION

Patients will receive either reparixin at a dose of 2.772 mg/kg body weight/hour for 7 days (168 hrs) or matched (flow rate/length of infusion) placebo, according to the randomization number.

The dosing solution (if reparixin, 11mg/mL) will be administered as a continuous i.v. infusion into a (high flow) central vein, by an infusion pump adequate to provide reliable infusion rates (see below), as per treatment schedule.

Infusion of the Investigational Product will start approximately 12hrs (allowed range 6-18hrs) before the anticipated time when islet infusion is started. The Investigator will identify the time to start study drug administration.

The pump rate will be adjusted to provide an infusion rate of approximately 0.25mL/kg/hour. Actual infusion rate (mL/hour), adjusted to body weight, is tabulated in [Appendix 14.3](#). Figures in the appendix represent mathematical rounding of original infusion rates derived from the following formula:

$$\text{Infusion rate (mL/hour)} = \frac{\text{dose (mg/kg/hour)} \times \text{body weight (kg)}}{11.00 \text{ mg/mL}}$$

Such a rounding affects actual administered dose/kg/hour by less than 1%.

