## 6 ANALYSIS POPULATIONS

Five analysis populations will be identified and used in the summarization and analysis of data, namely all screened patients, all randomized patients, intent to treat, per protocol, and safety.

- All Screened Patients: This population will include all patients screened for participation in the trial.
- All Randomized Patients: This population will include all patients randomized to investigational product in the trial.
- Intent to Treat: This population will consist of all patients who are randomized and receive the investigational product (either reparixin or placebo). Summarization and analysis of this population will be based on randomized treatment, regardless of treatment actually received. Eligible patients will be included in this population whether or not they receive IAT, because exclusions cannot be made for events occurring after randomization that could be influenced by the randomized assignment.
- Per Protocol: This population will consist of all patients in the ITT population who meet all of the following criteria:
  - Received IAT
  - Completed 7 days of investigational product dosing
  - No major protocol violations, including violations of inclusion/exclusion criteria, errors in treatment assignment, use of prohibited medication, etc.
  - Visits occurring on Day 75 ± 14 days from IAT and Day 365 ± 14 days from IAT
  - Insulin-independence status recorded at Day 365 ± 14 days from IAT

Further criteria for exclusion from the PP population may be identified during the data review meeting held prior to database lock.

- Safety: This population will consist of all randomized patients. Summarization and analysis of this population will be based on treatment actually received.

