#### **7.7.1 Inflammatory Chemokines/Cytokines**

Inflammatory chemokines/cytokines to be summarized include serum levels of CXCL8, CCL2 (MCP-1), CCL3, CCL4, CXCL10 (IP-10), CXCL9 (MIG), IL-6, IL-10, INF- $\gamma$ , TNF- $\alpha$ , and IL-1 $\beta$ . Values are collected as 2 basal samples at pre-infusion hospital admission (6 to 24 hours apart) and at 6, 12, 24, 72, 120, and 168 hours after IAT.

Observed values at each time point and baseline (the average of the two basal samples) and change from baseline (follow-up value minus baseline value) at each post-transplant time point will be summarized descriptively by treatment group and in total.

Observed values will also be presented as box plots for each treatment group at each time point in order to graphically examine the time course of each parameter for each treatment group.

The relationship between inflammatory chemokines/cytokines response (including AUC, peak level, and maximum change from baseline) and exposure to reparixin may be explored graphically, with inflammatory chemokines/cytokine response plotted against total reparixin dose (in mg/kg) received.

REP0112

Statistical Analysis Plan

- Area under the curve will be computed as follows. When parameter values are below the limit of detection, an appropriate value will be assumed in the calculation of area under the curve. Missing parameter values will be imputed via linear interpolation, and the average of the two basal samples (values, and mid-point of the sample times) will be used as the first sample in the computation of the AUC. Once these rules have been applied to the data, AUC for a parameter will be computed using the trapezoidal rule. For ease of interpretation, the AUC value obtained will be divided by the total time the scale is assessed for reporting purposes. Computation of AUC will be based on actual collection times, unless actual collection time is missing, in which case the scheduled collection time will be used.
- Peak level for any given inflammatory chemokine/cytokine parameter will be the maximum post-baseline value, where the baseline value will be the average of the two basal values.
- Maximum change from baseline for any given inflammatory chemokine/cytokine parameter will be the greatest change from baseline value, where change from baseline is computed as a post baseline value minus the baseline value and where baseline value is the average of the two basal values.

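### SAP 7.4.7 converts infused mL to mg at 11.00 mg/mL with no exception for placebo, so saline patients would be tabulated with milligrams of a drug they did not receive

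*SAP*

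**What the plan says.** SAP 7.4.7 (Investigational Product Exposure) covers the safety population. It lists duration, average rate, amount infused and percentage of intended dose, and states how they are tabulated: "infused in mL and in mg, and percentage of intended dose administered will be summarized descriptively by treatment group and in total".

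The milligram rule is set per patient: "Amount of investigational product infused in mg will be estimated for a given patient for each infusion bag or over all infusion bags", namely as "the amount of investigational product infused in mL multiplied by 11.00 mg/mL (per Section 6.1.4 of the study protocol". No clause limits the rule to one arm.

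The term covers both arms. SAP section 6 defines the ITT population as "all patients who are randomized and receive the investigational product (either reparixin or placebo"), and protocol section 6 describes the product as reparixin "or matched placebo".

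The protocol ties the concentration to reparixin. Section 6.1.4, which the SAP cites, gives 11.00 mg/mL as the strength at which reparixin is dispensed after dilution. Section 6.2 makes the condition explicit: "The dosing solution (if reparixin, 11mg/mL"). For the other arm the synopsis says: "Placebo (0.9% w/v sodium chloride solution) will be infused at matching volume/rate".

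**The concern.** The conversion factor is a property of one arm's solution, but the SAP applies it to both. Because volume and rate are matched, the error is not a small contamination. It gives placebo patients a full nominal drug dose.

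The direct consequence is for Table 14.1.10 (Investigational Product Exposure). Under the stated rule the placebo column for mg would be false throughout, and the pooled column would mix real milligrams with milligrams that were never given. With 1:1 allocation and 100 to 105 patients planned, this concerns about half of them.

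A second place deserves care. SAP 7.7.1 allows cytokine response to be "plotted against total reparixin dose (in mg/kg) received", with figures listed for the safety population, which holds both arms. That section does not say how the dose is derived.

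**Working it through.** **Inputs**
- Vial: 33 mg/mL in 250 mL (protocol 6.1.1), made up to 750 mL with saline (6.1.4).
- Dose: 2.772 mg/kg/hour for 168 hours (6.2, Appendix 3).
- Infusion rates by weight: Appendix 3, which runs from 45 to 100 kg.
- Placebo: 0.9% sodium chloride (6.1.1) at matching volume and rate (synopsis).
- Body weight: the documents give no mean. I use 70 kg for illustration and the Appendix 3 limits as the range.
- Infusion time: a complete 168 hours is assumed.

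**Step 1. Reproduce the protocol's own figures.**
- Concentration: 33 × 250 / 750 = 11.00 mg/mL, as stated, for a bag made from a reparixin vial.
- Rate at 70 kg: 2.772 × 70 / 11 = 17.64 mL/hour. Appendix 3 shows 17.6, a rounding of −0.23%, within the protocol's stated limit of 1%.
- 24-hour volume: 17.6 × 24 = 422.4 mL, as in Appendix 3.

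**Step 2. Apply the SAP rule to a placebo patient.** Formula: mg = rate (mL/hour) × hours × 11.00.

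| Weight | Rate (mL/hour) | Volume over 168 h (mL) | mg under SAP 7.4.7 | True reparixin (mg) |
|---|---|---|---|---|
| 45 kg | 11.3 | 1,898.4 | 20,882 | 0 |
| 70 kg | 17.6 | 2,956.8 | 32,525 | 0 |
| 100 kg | 25.2 | 4,233.6 | 46,570 | 0 |

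A reparixin patient of the same weight and infusion time gets the same figure in the fourth column, where it is correct.

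**Step 3. The pooled total.** Take equal arms, 70 kg and complete infusions. As written, the pooled mean is (32.5 + 32.5) / 2 = 32.5 g. With placebo counted as 0 it is (32.5 + 0) / 2, about 16.3 g. Neither value describes the exposure of any patient group.

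**Step 4. Check the neighbouring derivation.** The percentage of intended dose is written as (2.772 × weight × duration) / (2.772 × weight × 168) × 100. Dose and weight cancel, leaving duration / 168 × 100. This measures infusion completion and is right in both arms. The numerator is a step in the derivation and is not among the variables to be summarised.

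**The case against.** The best defence is that the rule carries its own limit. It cites protocol 6.1.4, which speaks of reparixin, so an attentive programmer would see that the factor has no source for saline. The shell for Table 14.1.10 is also not in the text available, and it may show placebo as not applicable. A reader of a column headed Placebo would hardly take the milligrams for drug exposure.

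Part of this stands. Whether the final table would carry the error is not known, and the citation makes the intent guessable. But the SAP text asks for mg in each treatment group and pooled, for each patient, with no placebo exception. A rule that gives a false value when followed literally should not depend on the programmer departing from it.

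Two further inferences are tempting, and the documents do not support them.
- *That the cytokine plots would show placebo patients at a full drug dose.* SAP 7.7.1 names a different variable, reparixin dose in mg/kg, with no reference back to 7.4.7. On its plain meaning that dose is 0 for placebo. The plots are also optional.
- *That the percentage of intended dose is wrong for placebo.* Step 4 of the working shows that it is not.

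**Conclusion.** The point holds as a wrong derivation rule of limited reach. As written, SAP 7.4.7 assigns placebo patients the milligrams of a reparixin patient of the same weight and infusion time, where the true amount is 0, and it asks for a pooled total that cannot be interpreted.

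The size depends on weight and completeness of infusion. It is about 21 to 47 g over the Appendix 3 weights for a full 168 hours, and less for an interrupted or stopped infusion. The 32.5 g at 70 kg is an illustration and should not be read as an expected mean. The fault itself depends on neither assumption.

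The effect stays within exposure reporting. Volume, rate, duration and percentage of intended dose are sound in both arms, and no efficacy analysis, multiplicity rule or sample-size figure uses the milligram variable. This is a minor correction.

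**What to change.** In SAP 7.4.7:
- Compute and summarise the amount in mg only for patients who actually received reparixin, with placebo shown as 0 or not applicable.
- Drop the pooled total for mg.
- Leave volume, rate, duration and percentage of intended dose as they are, for both arms.

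In SAP 7.7.1, as a safeguard, add that if the dose plots are made, total reparixin dose is 0 for placebo patients or those patients are excluded.

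The cost is one sentence in each section and one condition in the program. The safety population is already analysed by treatment actually received, so the variable needed for the condition exists, and no new data are required.

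### SAP 7.4.7 takes interruption hours off a time in seconds, and its percentage of intended dose measures infusion time rather than dose; only descriptive exposure outputs are affected

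*SAP*

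**What the plan says.** SAP 7.4.7 summarises five exposure quantities by treatment group and in total.

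- **Duration.** Last infusion end minus first infusion start, "plus 1 second and minus the total interruption time in hours, divided by 3,600 seconds per hour".
- **Average rate.** The mean of the rates of all bags started.
- **mL infused.** Estimated "for each infusion bag as infusion rate in mL/hour multiplied by duration of investigational product infusion per bag", then summed over bags. The per-bag duration follows the same definition as above.
- **mg infused.** The "amount of investigational product infused in mL multiplied by 11.00 mg/mL".
- **Percentage of intended dose.** "Percentage of intended dose administered will be computed as duration of investigational product infusion in hours divided by 168 hours, multiplied by 100". The SAP shows its derivation: actual dose is 2.772 mg/kg × weight × duration, intended dose is 2.772 mg/kg × weight × 168 h, and the ratio is duration/168.

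The protocol supplies the context. Section 6.2 gives the dose per kg per hour for 168 h. Section 6.4.1 has the start, end and rate of each container entered in the CRF, with interruptions that exceed 30 minutes in total per 24 h. Section 7.1.2 allows a halt of up to 6 h during surgery. Section 6.3.1 foresees no dose modification. Section 6.1.1 defines placebo as saline.

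**The concern.** The duration formula adds 1 second and ends by dividing by 3,600 seconds per hour, so its numerator is in seconds. An interruption expressed in hours cannot be subtracted there. A program that follows the text would leave almost the whole interruption inside the infusion time. The protocol expects interruptions, so this is not a remote case.

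The percentage is labelled as dose, but its numerator assumes that the pump ran at the planned rate. Rate and weight cancel and only time remains. The mg amount in the same table is built from recorded bag rates, so the table would hold two versions of the dose received that need not agree.

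A smaller matter follows from the mg rule. Applied to both arms and to the total, it would assign mg of reparixin to patients who received saline.

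At stake is whether the exposure table describes delivery correctly.

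**Working it through.** **The SAP's own result.** (2.772 × kg × h)/(2.772 × kg × 168) = h/168. The algebra reproduces exactly, on the condition that the pump always ran at the planned rate.

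**Step 1: duration.** Let S be the clock span and I the interruption, both in hours.

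- As written: (3,600 × S + 1 − I)/3,600
- Consistent units: (3,600 × S + 1 − 3,600 × I)/3,600

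Subtracting I after the division gives the same value as the second line. Taking the span in hours instead does not rescue the text: (168 + 1/3,600 − 6)/3,600 = 0.045 h.

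| Span (h) | Interruption (h) | As written | Consistent units |
|---|---|---|---|
| 168 | 0 | 168.0003 h, 100.0% | 168.0003 h, 100.0% |
| 168 | 0.5 | 168.0001 h, 100.0% | 167.5003 h, 99.7% |
| 168 | 6 | 604,795/3,600 = 167.9986 h, 100.0% | 583,201/3,600 = 162.0003 h, 96.4% |
| 168 | 24 | 167.9936 h, 100.0% | 144.0003 h, 85.7% |
| 174 | 6 | 626,395/3,600 = 173.9986 h, 103.6% | 604,801/3,600 = 168.0003 h, 100.0% |

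The 6 h value is the limit in Protocol 7.1.2. The 0.5 h and 24 h values are illustrative. The last row is a halt that is made up by a later end; Appendix 5 allows ±12 h at the end of infusion. The overstatement is I × (1 − 1/3,600)/168 × 100, which is 3.57 points for 6 h and 14.28 points for 24 h.

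**Step 2: carry-over to mL and mg.** For 70 kg, Appendix 3 gives 17.6 mL/h. A 6 h halt leaves 6 − 6/3,600 = 5.998 h too much. That is 17.6 × 5.998 = 105.6 mL, or 105.6 × 11 = about 1,161 mg, against an intended 2.772 × 70 × 168 = 32,599 mg.

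**Step 3: rate, with the pump set from Appendix 3.** All tabulated rates from 45 to 100 kg equal 2.772 × kg/11 to one decimal. Delivered relative to planned dose is rate × 11/(2.772 × kg) − 1.

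- At whole-kg weights: −0.39% (49 kg) to +0.37% (51 kg).
- At the top of each weight band, which shares one rate: 45.99 kg gives 11.3 × 11/(2.772 × 45.99) − 1 = −2.50%; 100.99 kg gives 25.2 × 11/(2.772 × 100.99) − 1 = −0.98%.

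So a correctly set pump can deliver up to about 2.5% less than the percentage shows.

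**Step 4: rate, with the pump off plan (assumed values).** A 168 h infusion recorded at 90% or 75% of the planned rate shows 100% by the SAP formula. The mg amount for the same patient would be 90% or 75% of plan.

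**The case against.** The duration bullet is headed as hours and names the conversion factor, so its purpose is clear and a programmer would probably convert the units. That is likely, and it makes this a drafting error. The text remains the specification, though, and following it gives the wrong value. Where a halt is made up, a figure above 100% might also be noticed; where it is not made up, the figure is an unremarkable 100.0%.

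The percentage is openly derived and valid for a fixed-rate infusion with no dose modification foreseen. Most shortfalls would come from interruption or early stopping, which time is meant to capture. This stands in part: with the pump on Appendix 3 the gap is small. But no dose modification foreseen describes the plan, and an exposure table is meant to show whether delivery matched it.

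A reader might infer more than the documents support:

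- **That every exposure formula is wrong.** The average-rate formula is unaffected. The mL and mg formulas use recorded rates and inherit only the duration error, apart from the placebo mg label.
- **That the table cannot reveal under- or over-infusion.** It reports rate, mL and mg from recorded bag rates. These are not scaled to weight, so they are not a per-patient compliance figure, but the information is not discarded.
- **That surgical halts vanish from the report.** Section 7.4.7 separately counts patients with continuous infusion, and SAP 7.1 lists all CRF data.
- **That the cytokine figures are wrong.** SAP 7.7.1 says response may be "plotted against total reparixin dose (in mg/kg) received". The plots are optional and the section does not say which dose calculation feeds them. They would inherit the error only if a dose from 7.4.7 is used.

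**Conclusion.** Both errors hold as written, and both are minor. The duration formula removes only 1/3600 of each interruption: at the 6 h surgical limit it overstates by 3.57 percentage points, whether or not the time is made up. This rests on the literal reading; a program that converts the units shows no error.

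The percentage of intended dose is a percentage of intended time. Its error from rate is at most about 2.5% for weights in the Appendix 3 table with the pump set from it. It is larger only if recorded rates depart from the table, and the documents give no evidence of how often that happens; the 75% to 90% rates above are assumptions.

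The consequences are descriptive. A reader might infer a threat to the efficacy analysis or to the per-protocol set. The documents do not support that: no efficacy test uses these quantities, and the SAP Section 6 criterion of completing the 7-day infusion is not tied to this percentage.

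**What to change.** Amend SAP 7.4.7 as follows.

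1. **Duration, overall and per bag:** (end minus start in seconds + 1 − interruption in seconds)/3,600. Equivalently, convert the span to hours and then subtract the interruption in hours.
2. **Percentage of intended dose:** total mg infused, from recorded bag rates and corrected durations, divided by the Protocol 6.2 hourly dose × weight × 168 h, times 100. Write the unit as mg/kg/hour, since the derivation omits the per-hour part.
3. **Placebo:** compute the percentage from mL infused over planned mL, where planned mL/h is the Protocol 6.2 rate formula. The 11 mg/mL cancels, so this is the same ratio as in item 2 and serves both arms. Report no mg of reparixin for placebo or for the pooled total.

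If the time-based figure is still wanted, keep it under a label that says percentage of intended infusion time.

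The cost is about three lines of text and the matching program code. Bag times, rates and interruptions are already in the CRF, and weight is measured at screening. Nothing in study conduct changes.
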